#### **6.6.4. Concomitant Medications and Nondrug Treatments**

Prior drug and non-drug treatment, concomitant drug and non-drug treatment will be summarized according to CaPS.

### **6.7. Safety Summaries and Analyses**

The analysis population for safety is described in [Section 4](#). Safety and tolerability will be assessed by clinical review of all relevant parameters including adverse experiences (AEs), ECG, vital signs, local skin tolerability and laboratory tests. A complete list of laboratory parameters can be obtained in Appendix 2 of the protocol.

All the tables, listings and graphs for adverse events, lab parameters and vital sign and ECG will follow CaPS.

### 6.7.1. Adverse Events

AE endpoints including below will be listed and summarized in accordance with the CaPS:

- Treatment-emergent AEs , SAEs, treatment area AEs and treatment related AEs.
- Discontinuation of treatment due to AEs and treatment area AEs.

Table display will be by descending order of frequency in all treatment arms.

### 6.7.2. Laboratory Data

Laboratory data will be listed and summarized in accordance with the CaPS. . Categorical summaries of participants meeting pre-specified abnormality criteria will be created.

### 6.7.3. Vital Signs

The absolute value, and change from baseline will be summarized by treatment and time. Categorical summary of participants meeting pre-specified clinical criteria will be provided by treatment and time.

### 6.7.4. Electrocardiograms

The absolute value and changes from baseline for the ECG parameters QT interval, heart rate, QTc interval, PR interval, and QRS complex will be summarized by treatment and time.

The number (%) of participants with maximum post-dose QTc values and maximum increases from baseline in the following categories will be tabulated by treatment:

#### Safety QTc Assessment

Degree of Prolongation	Mild (msec)	Moderate (msec)	Severe (msec)
Absolute value	>450-480	>480-500	>500
Increase from baseline		30-60	>60

### 6.7.5. Local Skin Tolerability

Categorical summary tables will be provided by treatment and time. In addition, a summary of number and percent of participants by worst local skin tolerability grade during the whole study period will be created.

## 7. INTERIM ANALYSES

### 7.1. Introduction

An interim analysis may be performed to assess efficacy and safety when approximately 60% of the planned participants, i.e., approximately 25 participants per arm in AD and 18 participants per arm in PsO have completed or had the chance to complete Week 8 visit. Interim analysis results may be used for decisions regarding stopping for futility and internal program development. The detailed decision boundary will be detailed in the IRC charter. Additional interim analysis may be performed and will be detailed in the IRC charter.

### 7.2. Interim Analyses and Summaries

At interim, analyses specified in [Section 6.1.1](#) will be performed for IGA/PGA success and EASI/PASI-75 at week 8. In addition, safety data including primarily adverse event, tolerability and PK data will be analyzed.

Interim predictive probability of success (PoS) in primary endpoints based on the interim data will be calculated assuming a non-informative uniform prior for IGA/PGA success rate. The trial may stop for futility (non-binding) if the interim PoS <20%.

#### Interim Predictive Probability of Success

Let  $p_1$  and  $p_0$  be the probability of success for active arm and vehicle arm, both following a Beta(1,1) prior. Let  $s_{1i}$  and  $s_{0i}$  be the number of successes observed out of  $n_{1i}$  and  $n_{0i}$  participants at stage i for the active and vehicle arm.

For a given criteria at the end of stage 2: Posterior Prob(  $p_1 - p_0 > d | s_{12}, s_{02}, s_{11}, s_{01} > c$  ), where d is a target value and c is a probability cut-off to be detailed in IRC charter, since

$p_1|s_{11}, s_{12} \sim Beta(s_{11} + s_{12} + 1, n_{11} - s_{11} + n_{12} - s_{12} + 1)$

$p_0|s_{01}, s_{02} \sim Beta(s_{01} + s_{02} + 1, n_{01} - s_{01} + n_{02} - s_{02} + 1).$

we can calculate interim (stage 1) predictive probability of success of such criteria as

Predictive Prob {Posterior Prob (  $p_1 - p_0 > d | s_{12}, s_{02}, s_{11}, s_{01}$  )  $> c | s_{11}, s_{01}$  }

using below predictive distributions property:

$s_{12}|s_{11} \sim \text{Binomial}(n_{12}, p_1|s_{11})$ , and  $s_{02}|s_{01} \sim \text{Binomial}(n_{02}, p_0|s_{01})$ , where

$p_1|s_{11} \sim Beta(s_{11} + 1, n_{11} - s_{11} + 1)$  and  $p_0|s_{01} \sim Beta(s_{01} + 1, n_{01} - s_{01} + 1)$ .

Decision will primarily be based on interim data at week 8 and corresponding success criteria, as it is expected to have limited week 12 data at interim.

## 9. APPENDICES

### Appendix 1. Summary of Efficacy Analyses

Efficacy Endpoint	Analysis Type	Population	Data Inclusion and Rules for Handling Intercurrent Events and Missing Data	Analysis Model
Week 12 IGA / PGA Response	Primary	ITT	NRI	Chan & Zhang
	Sensitivity	ITT	NRI	Minimum Risk
	Supportive	ITT	NRI	Generalized Linear Mixed Model
	Supportive	ITT	NRI	Bayesian Emax
Week 12 EASI/PASI-75 Response	Secondary	ITT	NRI	Chan & Zhang
Week 12 PCFB in EASI / CFB in PASI	Secondary	ITT	MI	ANCOVA
PCFB in EASI / CFB in PASI	Sensitivity	ITT	OC	MMRM
PP-NRS Rate / IGA of clear or almost clear // PGA of clear or almost clear	Secondary	ITT	NRI	Chan & Zhang
CCI [REDACTED] [REDACTED]	Exploratory	ITT	NRI	Chan & Zhang

PCFB= Percent change from baseline; CFB= Change from baseline; ANCOVA = Analysis of Covariance; NRI = Non-Responder Imputation; OC = Observed Cases.

## Appendix 2. Dose Response Analysis for PsO

The 4-parameter Emax model will be fit using the latest version (currently v2.3.5) of the clinDR package. The below model will be applied the PGA success rate  $p$  at week 12.

$$\log \frac{p}{1-p} = E_0 + E_{max} \frac{d^\lambda}{d^\lambda + ED_{50}^\lambda}$$

### Weakly informative Priors Setup:

A weakly-informative prior distribution  $E_0 \sim t(\text{mean} = -2.44, \text{scale} = 4, \text{df}=5)$  gives a 31% probability  $p_0 < 1\%$  and 7% probability  $p_0 > 99\%$ , and is robust enough to cover the historical vehicle data range (4%~15%) for PGA success rate at week 6~12. The mean is based on meta-analysis results PGA success rate with a mean of 8% and 95% CI (4%,15%) at week 6~12, including the C3941002 study result with observed success rate of 1/17 (5.9%) and 95% CI (0.3%, 27.8%) at week 6.

We will specify the prior for the treatment effect  $E_T$  at a target dose (0.06% the maximum dose),  $E_T = E_{max} \frac{d_T^\lambda}{d_T^\lambda + ED_{50}^\lambda}$ . A prior distribution of  $E_T \sim t(\text{mean} = 1.23, \text{scale} = 2, \text{df}=5)$  will be used. C3941002 study at week 6 with observed PGA success rate of 3/17 (17.6%) for the low dose 0.01% and 1/17 (5.9%) for vehicle, results in an odds ratio of 3.43 with 95% CI (0.23, 191), or log odds ratio of 1.23 with 95% CI (-1.5,5.25). Such prior gives a 5% probability of log odds ratio > 5.25 (equivalent of a change in success rate from 8% to 94%), and a 39% probability of log odds ratio > 1.82 (equivalent of a change in success rate from 8% to 35%, the observed success rate at week 12 assuming observed treatment effect is linear in time), and 12% probability of log odds ratio < -1.5 (equivalent of a change in success rate from 8% to 2%).

**ED50:  $\log(ED50/P50) \sim t(\text{mean}=0, \text{scale}= 1.73, \text{df}=5)$ ,  $\text{Log}(\lambda) \sim t(\text{mean}=0, \text{scale}=0.425, \text{df}=5)$**  with a correlation of -0.45 between  $\log(\lambda)$  and  $\log(ED50)$  are the default prior in clinDR package, under which the probability of  $ED50/P50 > 32.6$  is 5%, and the probability of  $\lambda > 2.35$  is 5%.  $P50 = 0.02\%$  is empirically estimated as mean of the first two lowest dose.

The default MCMC burn-in and number of samples will be utilized, which will include 3 chains to assess convergence. Model diagnostics will be examined including trace and auto-correlations plots. If these raise concerns over model convergence, additional burn-ins, samples and thinning will be attempted to improve convergence. Non-monotone dose response relationship will be checked before model fitting.

An independent statistician will conduct QC of the analysis. The outputs of the analysis will be provided as .csv files to the programming team for inclusion with the tables and figures in the reporting.

### Appendix 3. Definition and Use of Visit Windows in Reporting

Visit windows will be used for efficacy variables, and for any safety data that display or summarize by study visit.

Visit No.	Visit Label	Target Day	Visit Window
	Screening	N/A	$-28 \leq \text{day} \leq -1$
1	Baseline*	1	$\text{day} = 1$
2	Week 1	8	$2 \leq \text{day} \leq 11$
3	Week 2	15	$12 \leq \text{day} \leq 22$
5	Week 4	29	$23 \leq \text{day} \leq 36$
6	Week 6	43	$37 \leq \text{day} \leq 50$
7	Week 8	57	$51 \leq \text{day} \leq 64$
8	Week 10	71	$65 \leq \text{day} \leq 78$
9	Week 12	85	$79 \leq \text{day} \leq 99$
10	FUP/EOS	N/A	$\text{day} > 99$

\* Baseline analysis visit window may be considered as  $\text{day} \leq 1$  in some analyses (e.g., those involving change from baseline). That is, in case that Day 1 observation is missing, the last observation before the first dosing date may be considered as the baseline. The baseline measurements for demography, height, pre-study medical history and medications will be collected at the "Screening" visit.

If two or more visits fall into the same window, keep the one closest to the Target Day. If two visits are equally distant from the Target Day in absolute value, the later visit should be used.

---

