#### 1.3.1. Atopic Dermatitis

Atopic Dermatitis												
Visit Identifier a  Abbreviations used in this table may be found in Appendix 13	Screening	Treatment Phase All assessments/procedures are pre-dose, unless otherwise stated									Follow-Up (EOS)	ET
		Day 1 (Baseline)	Week 1	Week 2	Week 4	Week 6	Week 8	Week 10	Week 12 (EOT)			
Visit Window	Day -28 to -1	N/A	Day 8 ±2	Day 15 ±2	Day 29 ±2	Day 43 ±2	Day 57 ±2	Day 71 ±2	Day 85 ±2	28–35 days post-last dose	NA	
Visit Number	1	2	3	4	5	6	7	8	9	10	NA	
Enrollment Procedures												
Informed consent/assent	X											
General medical and AD history	X	X										
Medication history	X	X										
Demography	X											
Eligibility assessment	X	X b										
Weight	X	X										
Height	X											
Clinical Assessments												
Physical examination c	X	X		X		X		X		X	X	
ECG	X	X								X	X	
Vital signs	X	X								X	X	
C-SSRS d	X											

Atopic Dermatitis												
Visit Identifier a  Abbreviations used in this table may be found in Appendix 13	Screening	Treatment Phase All assessments/procedures are pre-dose, unless otherwise stated									Follow-Up (EOS)	ET
		Day 1 (Baseline)	Week 1	Week 2	Week 4	Week 6	Week 8	Week 10	Week 12 (EOT)			
Visit Window	Day -28 to -1	N/A	Day 8 ±2	Day 15 ±2	Day 29 ±2	Day 43 ±2	Day 57 ±2	Day 71 ±2	Day 85 ±2	28–35 days post-last dose	NA	
Visit Number	1	2	3	4	5	6	7	8	9	10	NA	
AD-Related Clinical Assessments												
IGA	X	X	X	X	X	X	X	X	X	X	X	
EASI		X	X	X	X	X	X	X	X	X	X	
CCI												
BSA	X	X	X	X	X	X	X	X	X	X	X	
Laboratory Assessments												
Hematology, Chemistry and Urinalysis	X	X		X		X			X		X	
Serum FSH (WONCBP only)	X											
Serum Pregnancy Test (WOCBP only)	X											
Urine Pregnancy test f		X	X	X	X	X	X	X	X	X	X	
Pharmacokinetics												
CCI												
Biomarker Assessments												
CCI												
Retained Research Samples												
CCI												
Prep B1.5 (plasma)			X				X			X		
Prep B2.5 (serum)			X				X			X		
e-Diary												
Dispense e-diary and instruct on usage	X											

Atopic Dermatitis												
Visit Identifier a  Abbreviations used in this table may be found in Appendix 13	Screening	Treatment Phase All assessments/procedures are pre-dose, unless otherwise stated									Follow-Up (EOS)	ET

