## 7. DISCONTINUATION OF STUDY INTERVENTION AND PARTICIPANT DISCONTINUATION/WITHDRAWAL

### 7.1. Discontinuation of Study Intervention

It may be necessary for a participant to permanently discontinue study intervention. Reasons for permanent discontinuation of study intervention include the following: Liver injury, ECG changes, pregnancy, local tolerability, and AEs.

Note that discontinuation of study intervention does not represent withdrawal from the study. If study intervention is permanently discontinued, the participant will remain in the study to be evaluated for safety. See the [SoA](#) for data to be collected at the time of discontinuation of study intervention and follow-up for any further evaluations that need to be completed.

In the event of discontinuation of study intervention, it must be documented on the appropriate CRF/in the medical records whether the participant is discontinuing further receipt of study intervention or also from study procedures, posttreatment study follow-up, and/or future collection of additional information.

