#### **7.1.4. Local Tolerability**

If a participant experiences severity Grade 3 (severe) or 4 (very severe) on the local tolerability assessment ([Section 8.2.7](#)), study treatment will be discontinued permanently, and participant will proceed to ET visit and follow-up as described in [SoA](#).

If a participant experiences application site reaction of Grade 2 (moderate) on the local tolerability assessment, investigator may temporarily discontinue application of study intervention for up to 48 hours without consulting the sponsor. If in the clinical judgment of the investigator study intervention interruption beyond 48 hours is advisable, the investigator must obtain agreement from the Pfizer medical monitor to continue withholding study intervention. If temporary study intervention interruption for more than 5 consecutive days is

needed, then the participant should be permanently withdrawn from treatment and should follow up with the site until complete or near complete resolution of the AE. This dosing gap may occur only once for the same participant.

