### 3.2. Secondary Endpoint(s)

#### For AD:

- Proportion of participants achieving EASI-75 (75% improvement from baseline) at all study visit time points specified in the SoA.
- Proportion of participants achieving IGA score of clear (0) or almost clear (1) (on a 5-point scale) and a reduction from baseline of  $\geq 2$  points at all study visit time points specified in the SoA, except at Week 12.
- Percent CFB in EASI total score at all study visit time points specified in the SoA.
- Proportion of participants achieving IGA score of clear (0) or almost clear (1) at all study visit time points specified in the SoA.
- Proportion of participants having  $\geq 4$  points of reduction from baseline in weekly averages of PP-NRS at study visit time points specified in the SoA.
- Percent CFB in affected BSA at all study visit time points specified in the SoA.
- Incidence of treatment emergent AEs and SAEs, clinically significant changes in vital signs, ECG, and laboratory tests.
- Incidence of increase in local tolerability severity grades at times indicated in the SoA.

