## **5.3. Methods to Manage Missing Data**

### **5.3.1. Efficacy Data**

Analysis of binary data including primary endpoints will use the primary estimand (E1). All missing values, except missing due to COVID-19 pandemic, will be set to a failure ([Section 6.1.1](#)).

Continuous secondary endpoint analysis will use the secondary estimand (E2). For each landmark analysis (e.g., cross sectional analysis by week) missing data, except missing due to COVID-19 pandemic, will be imputed using a control-based imputation method ([Section 6.2.2](#)).

Summaries of tertiary/exploratory continuous data will use the observed data only and no additional considerations are needed.

If a participant misses a visit due to COVID-19, he/she will be excluded from the analysis for that visit; If a participant discontinues treatment or withdraws from the study due to

COVID-19, he/she will be excluded from the analyses after the treatment discontinuation visit or study withdrawal visit, respectively.

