## **6. ANALYSES AND SUMMARIES**

### **6.1. Primary Endpoint(s)**

#### **6.1.1. Main Analysis**

- Estimand strategy: Primary Estimand ([Section 2.2.1](#)). This estimand is intended to provide an estimate of the treatment effect in the absence of prohibited medication use in a population that may or may not be fully compliant with the treatment.
- Analysis set: ITT Analysis Set ([Section 4](#)).

- Analysis methodology: A landmark analysis of the IGA/PGA success endpoints at Week 12 will be performed using the ITT analysis set. The proportions responding and the corresponding risk difference comparing active treatment arm to vehicle group will be analyzed using the unconditional exact method; the risk differences and the corresponding 2 sided unconditional exact 95% confidence intervals will be computed using Chan and Zhang (1999) method. The overall family wise Type I error rate will be controlled at the 1 sided 0.025 level using the Hochberg step up procedure.
- Intercurrent events and missing data: A) Prohibited medication – response will be considered as failure for time points after start date of the event for participants who receive prohibited medication post randomization. B) Withdrawal and all other events, except COVID-19 pandemic, leading to missing data will be treated similarly assuming that participants no longer receive benefit from the study intervention and hence will be considered as failure. C) COVID-19 pandemic: if a participant misses a visit due to COVID-19, he/she will be excluded from the analysis for that visit; If a participant discontinues treatment or withdraws from the study due to COVID-19, he/she will be excluded from the analyses after the treatment discontinuation visit or study withdrawal visit, respectively. D) Inadequate compliance – participants data will be used as recorded.
- Proportions, risk differences and 95% confidence intervals will be presented.

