## **6.2. Secondary Endpoint(s)**

### **6.2.1. Binary Secondary Endpoints**

IGA/PGA success at other timepoints, EASI/ PASI-75, PP-NRS success ( $\geq 4$  points of reduction from baseline), IGA/PGA of clear or almost clear will be analyzed the same way as described in [Section 6.1.1](#). PP-NRS success rate will be summarized for all participants in ITT Analysis Set in AD, and adult participants (18–75 years old) only in ITT Analysis Set for PsO.

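### SAP Appendix 3 labels scores by study day alone, so an early stopper's attended Follow-Up is filed under Week 4 to Week 12 and counted as a missing failure at FUP/EOS (minor)

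*SAP*

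**What the plan says.** SAP Appendix 3 states: "Visit windows will be used for efficacy variables, and for any safety data that display or summarize by study visit". Week 12 is Day 79 to 99 (target Day 85) and FUP/EOS is any day after 99, with no target day. When two visits share a window, the one closest to the target day is kept. Neither the windows nor that rule looks at which visit produced the score.

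The Schedules of Activities (Protocol 1.3.1 and 1.3.2) place Follow-Up (EOS), visit number 10, at "28–35 days post-last dose". IGA, EASI and BSA (AD) and PGA, PASI and BSA (PsO) are all scored there.

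On stopping early, Protocol 7.1 says: "If study intervention is permanently discontinued, the participant will remain in the study to be evaluated for safety". For severe local reactions, Protocol 7.1.4 says: "participant will proceed to ET visit and follow-up as described in" the schedule.

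On analysis, SAP 3.2 lists among the AD secondary endpoints: "Proportion of participants achieving EASI-75 (75% improvement from baseline) at all study visit time points specified in the SoA". SAP 6.2.1 adds that "IGA/PGA of clear or almost clear will be analyzed the same way as described in" the main analysis. SAP 5.3.1 sets the missing-data rule for binary endpoints: "All missing values, except missing due to COVID-19 pandemic, will be set to a failure". SAP 6.1.1 ties failure after withdrawal to missing data: "Withdrawal and all other events, except COVID-19 pandemic, leading to missing data will be treated similarly".

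**The concern.** The FUP/EOS window is a fixed range of study days, but the visit it is meant to hold moves with the date of last dose. The two agree for completers and can disagree for early stoppers.

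Where they disagree, the participant came to Follow-Up and was scored, yet the FUP/EOS analysis sees no value. A binary endpoint then becomes a failure. A continuous endpoint is treated as missing and, where a landmark analysis is run, falls under control-based imputation. No estimand in the plan intends an attended visit to be handled as missing.

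A second effect follows from the same rule. The displaced score goes into another window, and for some stop dates that window is Week 12, the primary time point. Whether an early stopper has an observed Week 12 score or is a non-responder can then depend on the stop date alone.

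**Working it through.** **Inputs.** Day 1 is the first dose (SAP 3.4). The windows are from SAP Appendix 3: Week 4 is Day 23–36, Week 6 is 37–50, Week 8 is 51–64, Week 10 is 65–78, Week 12 is 79–99, and FUP/EOS is 100 or later. Follow-Up is 28 to 35 days after last dose. Completers take their last dose at the Week 12 visit (Protocol 6.1.1), Day 85 ± 2.

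**Completers.** Last dose Day 83 to 87 gives Follow-Up from 83 + 28 = Day 111 to 87 + 35 = Day 122. All are after Day 99, so the label is right.

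**Early stoppers.** With last dose on day L, Follow-Up is on Day L + 28 to L + 35.

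- Never FUP/EOS: L + 35 ≤ 99, so L ≤ 64.
- Always FUP/EOS: L + 28 ≥ 100, so L ≥ 72.
- Always Week 12: L + 28 ≥ 79 and L + 35 ≤ 99, so L = 51 to 64.

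| Last dose (day) | Follow-Up is labelled |
|---|---|
| 1 | Week 4 |
| 2–8 | Week 4 or 6 |
| 9–15 | Week 6 |
| 16–22 | Week 6 or 8 |
| 23–29 | Week 8 |
| 30–36 | Week 8 or 10 |
| 37–43 | Week 10 |
| 44–50 | Week 10 or 12 |
| 51–64 | Week 12 |
| 65–71 | Week 12 or FUP/EOS |
| 72 and later | FUP/EOS |

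This table needs no assumption beyond an on-time Follow-Up.

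**Week 12 examples.** Last dose Day 56 gives Follow-Up on Day 84–91, which supplies an observed Week 12 score 4 to 5 weeks off drug. Last dose Day 42 gives Day 70–77. Last dose Day 72 gives Day 100–107. If the ET visit is before Day 79 and no Week 12 visit is attended, neither of these two has a Week 12 value and both are failures. The Day 72 stopper was treated longer than the Day 56 stopper.

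**Size (assumed).** Take stop days even over Day 1–84 and the lag even over 28–35 days. Then 80.4% of stoppers' Follow-Ups lose the FUP/EOS label and 25.0% become Week 12 values. If stops are even over Day 43–84, the shares are 60.7% and 50.0%. If all stop by Day 43, they are 100% and 0%.

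The count per arm is N × stop rate × share, with every stopper attending Follow-Up:

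| Early stopping | FUP/EOS lost, AD (40) | FUP/EOS lost, PsO (30) | Week 12 from Follow-Up, AD | Week 12 from Follow-Up, PsO |
|---|---|---|---|---|
| 5% | 1.6 | 1.2 | 0.5 | 0.4 |
| 10% | 3.2 | 2.4 | 1.0 | 0.75 |
| 20% | 6.4 | 4.8 | 2.0 | 1.5 |

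If half attend, all counts halve.

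The shortfall in the FUP/EOS rate at 10% stopping is the lost visits × off-drug success rate ÷ N.

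- AD, success assumed 15% to 50%: 3.2 × 0.15 = 0.48 and 3.2 × 0.50 = 1.6. Over 40, that is 1.2 to 4.0 points.
- PsO, success assumed 8% to 50%: 2.4 × 0.08 = 0.19 and 2.4 × 0.50 = 1.2. Over 30, that is 0.6 to 4.0 points.

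The extra Week 12 successes per arm at 10% stopping are 1.0 × 0.15 to 0.50 = 0.15 to 0.5 (AD) and 0.75 × 0.08 to 0.50 = 0.06 to 0.4 (PsO).

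**Effect of one success at Week 12.** One-sided unconditional exact test, pooled score statistic, maximised over the common rate on a 0.001 grid, at counts near the planning rates:

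- AD: 20/40 vs 6/40, p = 0.0005; 19/40 vs 6/40, p = 0.0009; 20/40 vs 7/40, p = 0.0012.
- PsO (50% of 30 = 15; 8% of 30 = 2.4, taken as 2): 15/30 vs 2/30, p = 0.0001; 14/30 vs 2/30, p = 0.0002; 15/30 vs 3/30, p = 0.0004.

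All are below the strictest Hochberg step (0.025/2 = 0.0125 for AD, 0.025/3 = 0.0083 for PsO). With a weak effect one success can matter in either direction: PsO 7/30 vs 2/30, p = 0.046; 8/30 vs 2/30, p = 0.022; 8/30 vs 3/30, p = 0.058. Even 0.022 rejects under Hochberg only if both other doses also have p ≤ 0.025.

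**The case against.** The strongest reply concerns Week 12. The primary estimand is defined irrespective of compliance, so a score on Day 84–91 is a fair measure of status at about Week 12, whatever the visit is called. Replacing it with an imputed failure would be arguably worse. That stands. A reader might infer that the primary result, or every Week 4 to Week 12 rate, is wrong because it can contain Follow-Up scores. The documents do not support this. They do not restrict those windows to on-treatment data, and failure follows from missing data or prohibited medication, not from stopping.

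Nor would relabelling Follow-Up remove the dependence on stop date. An ET visit on Day 79 still gives a Week 12 score, while one on Day 78 does not.

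The path of early stoppers is also less certain than it looks. Only Protocol 7.1.4 spells out ET followed by Follow-Up. Protocol 7.2.1 keeps those who ask to stop the ointment in follow-up, in wording that may or may not include the Week 12 visit. If they attend it, the closest-to-target rule would normally select it for Week 12. That narrows the Week 12 point. It does not give Follow-Up its label back.

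Finally, FUP/EOS is a post-treatment time point with no multiplicity control, and no decision rule in the plan uses it. This is why the point is minor. It does not make the label correct.

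**Conclusion.** The FUP/EOS mislabelling holds. For last dose Day 1 to 64, and for some of Day 65 to 71, the rule as written files an attended Follow-Up elsewhere and scores the participant as a binary failure at FUP/EOS. Nothing in either document prevents it. The FUP/EOS rate in an arm can only be lowered by this, by about 1 to 4 points (AD) or 0.6 to 4 points (PsO) at an assumed 10% early stopping.

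At Week 12 the point is narrower. Using the Follow-Up score is defensible, but the plan should say whether it is intended instead of leaving the stop date to decide.

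The day arithmetic is exact. The counts rest on assumed stop rates, evenly spread stop days, full attendance and assumed off-drug success, and they are upper figures: prohibited-medication users are failures anyway and COVID-19 stoppers are excluded. The true numbers are probably small. The direction of any effect on the comparison between arms is unknown, because stoppers can be in any arm. One success either way changes no conclusion at the planning rates. Severity: minor.

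**What to change.** Add to SAP Appendix 3: *Assessments collected at the nominal Follow-Up (EOS) visit are assigned to FUP/EOS whatever the study day.*

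For Week 12, keep the main analysis the sponsor intends, but state whether an off-treatment Follow-Up score on Day 79 to 99 also counts as the Week 12 value. Run the other handling as one sensitivity analysis, and report per arm how many participants are affected.

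The cost is a few lines of SAP text and one extra run. No new data are needed, because Follow-Up already has its own visit number. The drawback is that FUP/EOS will pool a wider range of study days, from as early as Day 29 (last dose Day 1) to completers' Day 111–122.
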